4. OBJECTIVES AND ENDPOINTS

The objectives and endpoints are described in [Table 3](#).

Table 3: Objectives and Endpoints

Objectives	Endpoints
Primary	

 To evaluate the proportion of patients with obesity with genetic variants in a specific gene in the MC4R pathway who achieve a clinically meaningful reduction in body weight in response to setmelanotide at the end of open-label treatment 	
 The proportion of patients by genotype who demonstrate a significant clinically meaningful response (defined below) to setmelanotide at the end of Stage 1: 
 For all patients: achieving a $\geq 5\%$ reduction in BMI from Baseline
Secondary	

 To evaluate change in weight parameters and hunger in response to setmelanotide in patients with genetic variants in a specific gene in the MC4R pathway at the end of open-label treatment 	
 Mean change and percent change in BMI from Baseline to end of Stage 1 in all patients and patients ≥ 18 years old, per gene Mean change and percent change in body weight from Baseline to end of Stage 1 in patients ≥ 18 years old, per gene Mean change in BMI Z-score from Baseline to end of Stage 1 in patients < 18 years old, per gene Mean percent change in the weekly average of the daily maximal hunger score from Baseline to end of Stage 1 in patients ≥ 12 years old, per gene The proportion of patients ≥ 12 years old, per gene, who achieve a ≥ 2-point reduction (improvement) from Baseline to end of Stage 1 in the weekly average of the daily maximal hunger score
[REDACTED]	[REDACTED]
[REDACTED]	[REDACTED]

Table 3: Objectives and Endpoints

Objectives	Endpoints
[REDACTED]	[REDACTED]
[REDACTED]	[REDACTED]
[REDACTED]	[REDACTED]

Table 3: Objectives and Endpoints

Objectives	Endpoints
	
[REDACTED]
 
[REDACTED]
 
[REDACTED]
 
[REDACTED]
 
[REDACTED]
 
[REDACTED]
 
[REDACTED]
 
[REDACTED]
 
[REDACTED]
 
[REDACTED]

Safety	

 To evaluate the safety and tolerability of setmelanotide in patients with genetic variants in the MC4R pathway 	
 Safety and tolerability assessed by the frequency and severity of AEs, changes in vital signs, and changes in laboratory evaluations at the end of Stage 1 and Stage 2

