10.3. Statistical Analyses

A separate SAP will be developed, which will include a more technical and detailed description of the statistical analyses described in this section.

The primary efficacy endpoint of the trial is the proportion of patients by genotype who demonstrate a significant clinically meaningful response (defined below) to setmelanotide at the end of Stage 1:

- For all patients: $\geq 5\%$ reduction in BMI from Baseline

The 95% exact confidence interval will be provided for the primary efficacy endpoint. The analyses of the efficacy endpoints in Stage 1 will be performed based on the safety analysis set, and the analyses of the efficacy endpoints in Stage 2 will be performed based on the FAS, which is defined as all patients randomized in Stage 2 who received at least 1 dose of trial medication (placebo or setmelanotide) in Stage 2 and have baseline data.

AEs/SAEs will be summarized with frequencies and percentages. A by-patient AE data listing including onset and resolution dates, verbatim term, preferred term, treatment, severity, relationship to treatment, action taken, and outcome will be provided.

Safety data including laboratory evaluations and vital signs assessments will be summarized by time of collection. In addition, change from baseline to any post-dose values will be summarized for vital signs and clinical laboratory results. Frequency of patients with abnormal safety laboratory results will be tabulated.

All safety analyses and summary tables will be based on the safety analysis set.

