	
[REDACTED]
 
[REDACTED]
	
[REDACTED]
 
[REDACTED]
 
[REDACTED]
 
[REDACTED]
 
[REDACTED]
 
[REDACTED]
 
[REDACTED]
 
[REDACTED]

	
[REDACTED]
 
[REDACTED]
 
[REDACTED]
 
[REDACTED]
 
[REDACTED]
	
[REDACTED]
 
[REDACTED]
 
[REDACTED]
 
[REDACTED]
 
[REDACTED]
 
[REDACTED]
 
[REDACTED]
 
[REDACTED]
 
[REDACTED]
 
[REDACTED]
 
[REDACTED]

	
[REDACTED]
 
[REDACTED]
 
[REDACTED]
 
[REDACTED]
 
[REDACTED]
 
[REDACTED]
 
[REDACTED]
 
[REDACTED]
	
[REDACTED]
 
[REDACTED]
 
[REDACTED]
 
[REDACTED]

	
[REDACTED]
 
[REDACTED]
 
[REDACTED]
 
[REDACTED]
 
[REDACTED]
 
[REDACTED]
	
[REDACTED]
 
[REDACTED]
 
[REDACTED]
 
[REDACTED]
 
[REDACTED]
 
[REDACTED]
 
[REDACTED]
 
[REDACTED]
 
[REDACTED]

	Objectives	Endpoints
Safety	To evaluate the safety and tolerability of setmelanotide in patients with genetic variants in the MC4R pathway	Safety and tolerability assessed by the frequency and severity of AEs, changes in vital signs, and changes in laboratory evaluations at the end of Stage 1 and Stage 2

A. Estimand

Attribute	Description
Treatment	Setmelanotide
Population	Patients between ages of 6 and 65 with Specific Gene Variants in the Melanocortin-4 Receptor Pathway
Endpoint	Achieving a $\geq 5\%$ reduction in BMI from Baseline at the end of Stage 1
Intercurrent Events	For Discontinuation of randomized treatment or use of a rescue medication if any, Treatment policy strategy will be implemented.
Population-level Summary	Proportion of patients achieving a $\geq 5\%$ reduction in BMI from Baseline at the end of Stage 1

III. Study Design

A. Design Overview

This is a 2-stage (open-label stage followed by a randomized double-blind, placebo-controlled stage) Phase 2 trial of setmelanotide in patients with obesity with specific gene variants in the MC4R pathway. Approximately 100 patients between the ages of 6 and 65 years, inclusive, are planned to be enrolled in Stage 2 of the trial with up to 200 patients enrolled in Stage 1 (open-label).

Stage 1 (Open Label)

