If the year and month are present and only the day is missing, and the year and month is the same as the last study day then the day will be imputed as the last day of the study.

F. Genetic Diversity

It is possible that a patient may enter the trial with more than one eligible gene. In this situation, all eligible genes will be captured in the database. For analysis purposes, a single gene will be considered the "primary gene" for that patient, and the patient will be analyzed within that gene cohort. The primary gene will be defined as the eligible gene with the most

significant American College of Medical Genetics (ACMG) categorization (e.g., Pathogenic>Likely Pathogenic>Variant of Uncertain Significance [VUS]). If two or more eligible genes share the same most significant ACMG categorization, then the “primary gene” will be defined as the least prevalent gene and the patient will be analyzed within that gene cohort.

G. Multiple Study Centers

The study is a multicenter trial. Data from all study sites will be pooled for the purpose of analyses. No adjustment for study center is planned.

H. Covariate Adjustment in Primary Analysis

Covariate adjustment is not applicable for this study as there is not statistical testing for the primary analysis.

I. Data Safety Monitoring Board

The Data Safety Monitoring Board (DSMB) will meet periodically (i.e., every 3 months) to review the cumulative safety data from the study and will make a recommendation to continue or modify the study, if needed. The following unblinded data will be presented to the DSMB members:

- Demographics
- Disposition
- Adverse Events
- 12-Lead ECG
- Injection Site Evaluation
- Skin Examination
- Hyperpigmentation
- Fitzpatrick Classification Scale
- Inclusion/Exclusion Criteria
- Sexual Function (Male)
- Sexual Function (Female)
- Safety Laboratory Data
- Columbia-Suicide Severity Rating Scale
- Patient Health Questionnaire-9

J. Interim Analysis

An interim analysis will be performed when all patients have completed Stage 1 or terminated before Stage 1. All Stage 1 related analyses on this SAP will be summarized.

To avoid any potential bias due to patients still enrolled in the study at the time of the interim analysis, an unblinded team member at ██████████ will be involved in ensuring that any data of the Stage 2 are not included in the interim analysis.

K. Multiple Comparisons

There is no statistical testing planned in this study.

L. Analysis Set

- **Screened Population**

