For continuous outcome measure analyses, a weekly average score will be calculated as an arithmetic mean. The baseline score for Stage 1 will still be arithmetic mean of the available score values within 7 days before or on the first dosing (Day 1). For visits in [Scenario 2], [Scenario 3] and [Scenario 4], arithmetic mean of up to 7 measurements that are closest to and before the scheduled visit date will be calculated. For example, measurements taken between Day 1 (V1) to Day 14 (V2) will be labeled as Day 14 (V2) measurement on the table display.

N. Data Display Characteristics

Data displays produced for this study will include three types—summary tables, data listings, and figures. Unless stated otherwise, data listings will be produced for all recorded data. Summary tables will be produced as specified in following sections. Additional data listings will be produced for outcome measures that involve extensive procedures to derive the analyzed outcomes. Figures will be produced when specified in sections to follow.

Listings in general will be presented by gene cohort, stage, then treatment (active and placebo) unless otherwise specified.

Data listings will simply list the data recorded on the CRF or derived for each patient. When expedient, additional levels of ordering hierarchy may reflect subsets of assessments within patient. Data listings will not display patient initials.

Tables in general will be presented by stage unless otherwise specified. In which stage 1 will be presented by overall, each gene in SEMA 3 gene cohort, and gene cohort, stage 2 will be present by overall, each gene in SEMA 3 gene cohort, gene cohort, and treatment (active and placebo).

Tables may have either of two general layouts. When the greatest interest is in direct comparison of one treatment group with the other at particular times, different columns of a summary table will display the statistics for the different treatment groups. The placebo group statistics will be displayed to the left of the treatment group statistics. When the evolution of statistics over time is of greater concern than comparison at particular moments, a group of rows may be designated for the placebo group; the table columns would be designated for different summary statistics of interest. A subsequent group of rows would then be used for the treatment group. In this layout, a group of rows that represent a treatment group would generally be ordered chronologically.

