The summary statistics displayed will be a function of the type of data associated with the summarized assessment. Unless stated otherwise in relevant sections to follow, continuous data will be summarized with the number of nonmissing values, mean, standard deviation, minimum, first quartile (Q1), median, and maximum, third quartile (Q3). Categorical data will

be summarized with the number of nonmissing values and the numbers of values equal to each of the possible values. Percentages of patients with each of the possible values will be calculated from the number of patients in the corresponding analysis population, unless stated otherwise. Some continuous variables may also be grouped into categorical levels and evaluated in frequency tables.

O. Blinded Review of Data

After all study data have been collected but prior to examining any study outcome data by treatment group, the data will be reviewed by the study statistician to determine whether any clarifications or changes to the analysis plan are needed. Any revisions made to the analysis plan as a result of the blinded review of the data will be documented.

P. Software Version

All analyses will be conducted using SAS Enterprise Guide 7.1 (64-bit) or SAS version 9.4 (64-bit).

Q. Gene Cohort Analysis

Gene cohort in this SAP is defined as group of patients with specified primary gene(s). In details, please see below for the grouping:

Gene Cohort	Genotype
SEMA3 Pathway	NRP1, NRP2, PLXNA1, PLXNA2, PLXNA3, PLXNA4, SEMA3A, SEMA3B, SEMA3C, SEMA3D, SEMA3E, SEMA3F, SEMA3G
PHIP	PHIP
SIM1	SIM1
MAGEL2	MAGEL2
Other	TRPC5, MRAP2, HTR2C, KSR2, TBX3, LEP, ISL1, DNMT3A, MECP2, MC3R, CPE, RPGRIP1L, CREBBP, TUB

After a patient enrolls in the trial, the pre-identified primary gene is reconfirmed or may be reclassified with the [REDACTED] and manual blind review during the trial. A supplemental analysis with the re-confirmative classification of genes will be conducted.

VI. Patient Accountability

All patients in safety analysis set will be used for below analyses unless otherwise specified. The table and listing display for all analyses below will follow section V.N unless otherwise specified.

A. Patient Demographic and Baseline Characteristics

Patient demographic and baseline characteristics will include the patient's age [6 to <12, 12 to <18, and 18 to ≤65 years of age], sex [Child-bearing potential if female], ethnicity, race, weight

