Medical history will be coded using Medical Dictionary for Regulatory Activities (MedDRA) version 24.1 Medical history will be tabulated by system organ class and preferred term. A listing of medical history will be provided.

VII. Efficacy Analyses

The analysis of the efficacy endpoints in Stage 1 will be performed based on the safety analysis set, and the analyses of the efficacy endpoints in Stage 2 will be performed based on the full analysis set (FAS). End of Stage 1 in below section will refer to the measurement collected at Week 16 and end of Stage 2 will refer to Week 40, unless otherwise specified. The tabulation and listing formats for all analyses below will follow section V.N unless otherwise specified.

A. Efficacy Assessments

A.1 Weight

Weight should be measured after patients have attempted to empty their bladders and after fasting for at least 8 hours. Patients are to wear light clothing or underwear and no shoes, with empty pockets and will be weighed at approximately the same time of day. All measurements will be recorded to the nearest 10th of a kg if reported with a digital scale, or half kg with a mechanical scale. Weight measurements will be collected in triplicate. Only in-person visits measurements will be summarized in tables.

[REDACTED]

[REDACTED]

[REDACTED]

[REDACTED]

[REDACTED]

[REDACTED] (Confidential) [REDACTED] [REDACTED]

[REDACTED]
[REDACTED]
[REDACTED]

[REDACTED]
[REDACTED]
[REDACTED]

[REDACTED]
[REDACTED]

[REDACTED]
[REDACTED]

[REDACTED]
[REDACTED]

[REDACTED]
[REDACTED]
[REDACTED]
[REDACTED]

[REDACTED]
[REDACTED]

[REDACTED]
[REDACTED]
[REDACTED]
[REDACTED]

[REDACTED]
[REDACTED]
[REDACTED]
[REDACTED]

[REDACTED]
[REDACTED]
[REDACTED]
[REDACTED]

[REDACTED]
[REDACTED]

[REDACTED]

[REDACTED]

[REDACTED]

VIII. Questionnaires

All patients in safety analysis set will be used for below analyses in Stage 1 and FAS in Stage 2 unless otherwise specified. The tabulation and listing formats for all analyses below will follow section V.N unless otherwise specified.

[REDACTED]

[REDACTED]

[REDACTED]

[REDACTED]

[REDACTED]

[REDACTED]

[REDACTED]

[REDACTED]

[REDACTED]

[REDACTED]

[REDACTED]

[REDACTED]

[REDACTED]

[REDACTED]

[REDACTED]

[REDACTED]

[REDACTED]

[REDACTED]

[REDACTED]

[REDACTED]

[REDACTED]

[REDACTED]

[REDACTED]

[REDACTED]

[REDACTED]

[REDACTED]

[REDACTED]

[REDACTED] (Confidential) [REDACTED] [REDACTED]

[REDACTED]
[REDACTED]
[REDACTED]
[REDACTED]
[REDACTED]

[REDACTED]

[REDACTED]

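### The primary endpoint is response by genotype, but the SAP's visible default table rule gives its own Stage 1 row to only 16 of the 30 eligible genes, and the estimand summary has no gene split

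*SAP*

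**What the plan says.** **Protocol.** Section 10.3 states: "The primary efficacy endpoint of the trial is the proportion of patients by genotype who demonstrate a significant clinically meaningful response", where response is a reduction in BMI of at least 5% from Baseline at the end of Stage 1. It adds: "The 95% exact confidence interval will be provided for the primary efficacy endpoint". In Table 3 (section 4) the primary objective concerns variants in a specific gene. The secondary endpoints are per gene; the hunger-responder endpoint, for example, covers patients at least 12 "years old, per gene, who achieve a" 2-point improvement.

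**SAP.**
- V.N, Data Display Characteristics, sets the general table layout: "stage 1 will be presented by overall, each gene in SEMA 3 gene cohort, and gene cohort". It is a default that other sections may override.
- V.Q defines five gene cohorts: SEMA3 Pathway, PHIP, SIM1, MAGEL2 and Other. Other contains "TRPC5, MRAP2, HTR2C, KSR2, TBX3, LEP, ISL1, DNMT3A, MECP2, MC3R, CPE, RPGRIP1L, CREBBP, TUB".
- VII, Efficacy Analyses, adopts that layout: "The tabulation and listing formats for all analyses below will follow section V.N unless otherwise specified".
- The estimand table gives as its population-level summary "Proportion of patients achieving a $\geq 5\%$ reduction in BMI from Baseline at the end of Stage 1".
- V.F, Genetic Diversity, gives each patient one primary gene. For tied classifications, the primary gene "will be defined as the least prevalent gene and the patient will be analyzed within that gene cohort".

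**The concern.** The protocol's unit of inference is the single gene. Genotype cannot easily be read as pooled cohort: V.Q has separate columns for cohort and genotype and lists individual genes under genotype. Protocol 5.1.4 also makes the gene the decision unit, since the sponsor may resize or close a gene cohort after assessing as few as 3 patients.

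The SAP's visible layout works at a different level for nearly half the genes. If nothing overrides it, three things follow:

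- For 14 genes no responder proportion and no exact interval are planned, although the protocol promises both. Other is a residual group, so its pooled rate describes no particular gene and can mask one that responds.
- Gene cohort has two meanings. In V.F it is the cohort of a single primary gene; in V.Q it is one of five groups. For a patient whose tied genes both fall in Other, the V.F tie-break changes no table.
- The supplemental analysis in section X inherits the layout. A patient reclassified from one Other gene to another would change no row.

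The interim analysis (V.J) summarises all Stage 1 analyses, so the default would reach that report first. Protocol section 10 says that major changes to the primary endpoint's definition or analysis will also appear in a protocol amendment, and the current protocol still says by genotype.

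**Working it through.** The documents give no figure to reproduce here. The check is a count of genes, followed by illustrations of what pooling hides and what gene-level rows would show.

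**1. Gene count.** Inputs: the list in Protocol Appendix 1, the list in SAP III.D and the cohort table in SAP V.Q, matched by name.

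- Appendix 1 names 30 distinct genes. SAP III.D names the same 30 plus a catch-all entry, not counted here.
- V.Q covers each of the 30 once:

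| Cohort | Genes | Own Stage 1 row under V.N |
|---|---|---|
| SEMA3 Pathway | 13 | 13 |
| PHIP, SIM1, MAGEL2 | 3 | 3 |
| Other | 14 | 0 |
| Total | 30 | 16 |

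- Share without a row: 14/30 = 47%.
- Display groups now: 1 overall + 13 genes + 5 cohorts = 19. With every gene shown: 19 + 14 = 33.

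This reads the SEMA3 cohort in V.N as the 13-gene SEMA3 Pathway in V.Q, which is the natural reading. If only SEMA3A to SEMA3G were meant, 7 + 3 = 10 genes would have a row.

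**2. Possible numbers of patients.** Planned enrolment is 100 to 200 (Protocol 10.1). Assume an even spread over 30 genes:

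- Per gene: 100/30 = 3.3 to 200/30 = 6.7.
- In Other: 14 × 3.33 = 47 to 14 × 6.67 = 93.

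**3. Dilution.** If one gene's response rate exceeds that of the rest of Other by d points and the gene supplies a share w of Other's patients, the pooled rate rises by w × d. Assume d = 60:

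| Share w | Rise in pooled rate (points) |
|---|---|
| 5% | 0.05 × 60 = 3.0 |
| 1/14 (equal shares) | 60/14 = 4.3 |
| 25% | 0.25 × 60 = 15.0 |

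**4. What a gene-level row would show.** Exact (Clopper-Pearson) 95% limits. For 0/n the upper limit is 1 − 0.025^(1/n); for n/n the lower limit is 0.025^(1/n).

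| n | 0/n | n/n |
|---|---|---|
| 3 | 0 to 70.8% | 29.2 to 100% |
| 7 | 0 to 41.0% | 59.0 to 100% |
| 10 (per-gene target, Protocol 5.1.4) | 0 to 30.8% | 69.2 to 100% |

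Mid-range results say less: 5/10 gives 18.7 to 81.3%.

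**5. Estimand.** The population attribute mentions specific gene variants only to describe who is included. The endpoint and summary attributes define one proportion. Nothing visible in the table splits it by gene.

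**The case against.** The strongest objection is the redaction. V.N is only a general layout, and it leaves the choice of summary tables to later sections. Section VII is blacked out after the weight assessment. The protocol's exact interval is also absent from the visible SAP, which suggests that the wording of the primary analysis lies in the hidden text; a per-gene table may be there too. The start of the SAP's objectives table is not visible either, and it may say by genotype. This stands. The point therefore concerns the visible default, and it cannot be claimed that no per-gene table exists.

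The magnitudes are also open to challenge. The 47% is a share of gene names, not of patients. Even enrolment is unlikely, because genes differ in prevalence and the sponsor may pause or close cohorts, so Other could be much smaller than 47 to 93. The 60-point difference has no source in the documents. All of this is fair, but the finding rests on the gene count and not on these illustrations.

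Finally, the practical loss is limited. Listings and the baseline genotype tabulation keep the data, no hypothesis test is planned, and intervals for 3 to 7 patients are wide. Age-restricted secondary endpoints will be sparser still. These points limit the importance but do not remove the mismatch: a listing is not a prespecified proportion with its interval, and the SAP already accepts sparse rows for the 13 SEMA3 genes.

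**Conclusion.** The concern holds. As visible, the SAP's default rule does not deliver the protocol's by-genotype primary endpoint for 14 of 30 eligible genes (47%), nor the per-gene secondary endpoints for those genes. The count rests only on the published gene lists and the natural reading of the SEMA3 cohort; a narrower reading would leave 20 genes without a row.

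Two parts do not depend on the unseen analysis text: the estimand's summary carries no gene split, and V.F and V.Q use gene cohort in different senses. The table point is conditional on no redacted section overriding V.N, so confidence in it is moderate. The patient numbers and dilution figures rest on the stated assumptions and only illustrate scale. The defect affects planned summaries and not data collection. It should be corrected, but it does not threaten the trial's conduct.

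**What to change.** - **V.N:** tabulate the primary and secondary Stage 1 endpoints for every enrolled primary gene, including each gene in Other, with n/N and the exact 95% interval for proportions. Keep the Other and overall rows as descriptive summaries. If a redacted section already does this, a cross-reference in V.N is enough.
- **Section X:** use the same rows for the supplemental analysis, so that reclassification within Other is visible.
- **Estimand table:** state that the population-level summary is by primary gene.
- **V.F:** say primary gene where a single gene is meant, and keep gene cohort for the five groups in V.Q.

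The cost is up to 14 extra rows in each Stage 1 efficacy table and its supplemental version, plus these wording edits. No extra data are needed. No multiplicity arises, because V.K plans no statistical testing. Many rows will be sparse, with wide intervals (0/3 gives 0 to 70.8%), and the age-restricted secondary endpoints will have fewer patients still. Each row should show its n and be read with that in mind.
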